#### 9.4 STATISTICAL ANALYSES

##### 9.4.1 GENERAL APPROACH

##### 9.4.2 ANALYSIS OF THE PRIMARY EFFICACY ENDPOINT(S)

Participants will be contacted one week after receiving treatment by the providing pharmacist to evaluate symptoms and bleeding. If the participant history suggests any concern for a continuing pregnancy, ectopic pregnancy or worrisome bleeding they will be referred to the UCSD Family Planning

Division where they will be scheduled for an ultrasound in clinic with a physician and further evaluation as indicated in a timely fashion. If the participant does not indicate any concern for a continuing pregnancy or ectopic pregnancy and is having appropriate bleeding, they will be instructed to use the high sensitivity urine pregnancy test four weeks after taking their misoprostol. This is a standard method for follow up supported by the American College of Obstetricians and Gynecologists. If the participant's first high sensitivity urine pregnancy test is positive but they have no symptoms concerning for ongoing pregnancy, they will be instructed to perform a second, high sensitivity urine pregnancy test in one week. If the second, high sensitivity urine pregnancy test is also positive, the patient will be evaluated by a physician and ultrasound or serial serum HCGs will be utilized if indicated.

#### 9.4.3 ANALYSIS OF THE SECONDARY ENDPOINT(S)

Following completion of study recruitment and patient visits, we will continue our study by performing in-depth semi-structured interviews with the participating patients and pharmacists to understand their experiences. The interviews will be analyzed using directed content analysis.

#### 9.4.4 SAFETY ANALYSES

AEs and SAEs will be recorded by the study team when they become aware. Adverse events leading to premature discontinuation from the study intervention and serious treatment-emergent AEs will be presented in a table.

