In congruency with a "no test" protocol published by the Society of Family Planning, Rh typing and administration of anti-D immunoglobulin will not be performed if the patient reports a positive Rh type, if the patient does not desire future childbearing or if the patient declines. For all other patients, they will be offered Rh typing and administered anti-D immunoglobulin as indicated. The blood typing and Rhogam administration will be ordered and administered by the participating pharmacists. Patient participants will be provided with two high sensitivity urine pregnancy tests to be used four weeks after the abortion as well as a patient instruction sheet that will include symptoms for which to call their abortion provider. These symptoms will include severe pain, pain not responsive to provided analgesics, bleeding soaking 2 maxi pads an hour for two consecutive hours, multiple clots the size of an egg or greater, dizziness or vomiting lasting more than 2 hours, an increase in bleeding or pain 24 hours after taking the misoprostol, fever of 100.4°F or higher 24 hours or more after taking the misoprostol and vomiting within 30 minutes of taking the misoprostol. The patients will be provided with written instructions about when to call and the emergency phone numbers to reach a UCSD provider. The participating pharmacist will provide a pager number and will be the initial provider available for questions and concerns with immediately available support from the UCSD family planning physicians as indicated. The family planning fellow will also be available to the pharmacists and patients at all times via the paging system for concerns or questions. Post-abortion contraception will be available to the patient by prescription from the pharmacist for oral contraceptive pills, contraceptive rings, the contraceptive patch or Depo Provera. Patient electing for intrauterine devices, contraceptive implants or sterilization will be scheduled for an appointment with a physician. Participants will be reimbursed a \$40 electronic gift card for their time and participation.

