Pharmacists' involvement in this pilot project will be conducted under a collaborative practice agreement (CPA). UCSD has an established history of CPAs across a variety of clinical services including HIV care, anticoagulation and transplant medicine. Under the agreement with a supervising physician, pharmacists can prescribe provide care for specified conditions. CPAs are utilized in some form in all states except for Delaware, and 36 states are currently allowing pharmacists to initiate patient medications in outpatient setting via CPAs. The pharmacists providing the medication abortions are not investigators nor research team members on this study.

Following completion of study recruitment and patient visits, we will continue our study by performing in-depth semi-structured interviews with the participating patients and pharmacists to understand their experiences. In addition, we will elicit feedback about ways to refine the toolkit to support the scale up of pharmacist provision of medication abortion in the future. We will follow a prepared interview guide (See Appendix A and Appendix B) The interviews will be analyzed using directed content analysis.

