## 7 STUDY INTERVENTION DISCONTINUATION AND PARTICIPANT DISCONTINUATION/WITHDRAWAL

### 7.1 DISCONTINUATION OF STUDY INTERVENTION

If a participant chooses not to move forward with pharmacist provision of medication abortion, she will be offered scheduling in either a UCSD Family Planning clinic for abortion care or in an obstetric clinic for ongoing obstetric care.

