## 8 STUDY ASSESSMENTS AND PROCEDURES

### 8.1 EFFICACY ASSESSMENTS

Participants will be contacted one week after receiving treatment by the providing pharmacist to evaluate symptoms and bleeding. If the participant history suggests any concern for a continuing pregnancy, ectopic pregnancy or worrisome bleeding they will be referred to the UCSD Family Planning Division where they will be scheduled for an ultrasound in clinic with a physician and further evaluation as indicated in a timely fashion. If the participant does not indicate any concern for a continuing pregnancy or ectopic pregnancy and is having appropriate bleeding, they will be instructed to use the high sensitivity urine pregnancy test four weeks after taking their misoprostol. This is a standard method for follow up supported by the American College of Obstetricians and Gynecologists. If the participant's first high sensitivity urine pregnancy test is positive but they have no symptoms concerning for ongoing pregnancy, they will be instructed to perform a second, high sensitivity urine pregnancy test in one week. If the second, high sensitivity urine pregnancy test is also positive, the patient will be evaluated by a physician and ultrasound or serial serum HCGs will be utilized if indicated.

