#### 8.3.4 TIME PERIOD AND FREQUENCY FOR EVENT ASSESSMENT AND FOLLOW-UP

The occurrence of an adverse event (AE) or serious adverse event (SAE) may come to the attention of study personnel during study visits and interviews of a study participant presenting for medical care, by communication from the participant to the study team, or upon review by a study monitor.

All AEs including local and systemic reactions not meeting the criteria for SAEs will be captured. Information to be collected includes event description, time of onset, clinician's assessment of severity, relationship to study product (assessed only by those with the training and authority to make a diagnosis), and time of resolution/stabilization of the event. All AEs occurring while on study must be documented appropriately regardless of relationship. All AEs will be followed to adequate resolution.

Any medical condition that is present at the time that the participant is screened will be considered as baseline and not reported as an AE. However, if the study participant's condition deteriorates at any time during the study, it will be recorded as an AE. Changes in the severity of an AE will be documented to allow an assessment of the duration of the event at each level of severity to be performed. AEs characterized as intermittent require documentation of onset and duration of each episode.

At each study visit, the investigator will inquire about the occurrence of AE/SAEs since the last visit. Events will be followed for outcome information until resolution or stabilization.

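### The one planned safety table omits non-serious adverse events in patients who stay in the pilot, and no hand-off of the pharmacist's follow-up findings to the AE record is stated

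*Combined protocol and SAP*

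**What the plan says.** **Collection.** Section 8.3.4 is broad: "All AEs including local and systemic reactions not meeting the criteria for SAEs will be captured". It asks for a description, onset, severity, relationship and resolution for each event, and adds: "At each study visit, the investigator will inquire about the occurrence of AE/SAEs since the last visit". Section 8.3.5 sends all AEs to the IRB.

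**Reporting as a study result.** Section 9.4.4 makes the study team's awareness the trigger for recording an event, and then plans one display: "Adverse events leading to premature discontinuation from the study intervention and serious treatment-emergent AEs will be presented in a table".

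**Discontinuation.** Section 6.1 names the intervention as pharmacist provision of medication abortion. Section 7.1 describes discontinuation as the participant's choice: "If a participant chooses not to move forward with pharmacist provision of medication abortion, she will be offered scheduling" with a UCSD clinic. Section 4.1 also lets a participant leave the pilot for physician care at any time.

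**Who hears of events.** Section 4.1 says: "The participating pharmacist will provide a pager number and will be the initial provider available for questions and concerns". The reasons to call are listed there: "These symptoms will include severe pain, pain not responsive to provided analgesics", followed by bleeding, clots, fever, vomiting and others. Section 8.1 adds: "Participants will be contacted one week after receiving treatment by the providing pharmacist to evaluate symptoms and bleeding". The same follow-up text stands in sections 4.1 and 9.4.2. Section 4.1 also says: "The pharmacists providing the medication abortions are not investigators nor research team members on this study".

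**The concern.** The plan collects more than it intends to show. Section 2.3.2 presents the pilot as a source of preliminary data on a new care model and of support tools for a larger pilot. Section 4.1 expects follow-up protocols to be part of the toolkit under test. Non-serious events that a pharmacist manages, or passes on to a physician, are direct evidence on whether that follow-up works. They are also the events that the safety table leaves out.

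The routing adds to this. If the person who first hears of an event is outside the research team, and recording starts only when the team knows, the completeness of the AE record depends on a transfer that the plan does not describe. An event that never reaches the record reaches neither a listing nor the IRB.

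**Working it through.** No calculation in the plan bears on this. Section 9.1 states no hypothesis, section 9.2 gives 10 patients as a convenience sample, and no AE rate is assumed. The check is a reading of the sections against each other.

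**Step 1: what the table admits.** Take a patient with a fever after misoprostol who is managed as an outpatient, recovers and completes the pilot.

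- Serious under section 8.3.2? No. There is no death, threat to life, admission, lasting incapacity or birth defect, and no intervention to prevent one.
- Leading to discontinuation? No. Section 7.1 describes a participant's decision not to go ahead, and section 7.2 says the team withdraws nobody unless the participant asks. Referral to a physician for evaluation is not described as discontinuation.

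The event meets neither criterion, so it is not in the table.

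**Step 2: whether it appears in another planned result.**

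| Section | Content | Summarises such an event? |
|---|---|---|
| 8.3.4, 8.3.5 | Collection; reporting to the IRB | No, neither is a study result |
| 9.4.1 | No text | No |
| 9.4.2 | Repeats the follow-up procedure | No summary of symptoms is named |
| 9.4.3 | Content analysis of interviews | Only if it comes up as an experience |
| 9.4.4 | Serious and discontinuation AEs | No |

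**Step 3: size.** Let k be the number of patients whose only AEs are of this kind. The documents do not fix k, so 0 ≤ k ≤ 10. Each such patient is 1/10 = 10% of the sample. Section 4.1 lists eight reasons to call, but these are prompts to telephone, not AE definitions, and they give no estimate of k.

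**Step 4: contacts from the pharmacist visit onward.**

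| Contact | With whom | Comment |
|---|---|---|
| Telehealth visit (4.1) | Physician prescriber | Before mifepristone, so it cannot pick up post-dose events |
| Pager (4.1) | Pharmacist first; fellow also reachable | Default route is the pharmacist |
| One week (8.1) | Pharmacist | Referral for suspected continuing or ectopic pregnancy, or worrisome bleeding |
| Four-week urine test (8.1) | Done by the participant | Physician if a second test is positive |
| Post-pilot survey and interview (4.2, 9.4.3) | Research team | After recruitment and patient visits |

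No routine investigator visit after treatment is described to which the section 8.3.4 enquiry could attach. That section names study visits, interviews, communication from the participant and monitor review as ways in which events become known. A report from the pharmacist is not among them.

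**The case against.** **On the table.** Pain, heavy bleeding, nausea, vomiting, diarrhea and headache are listed in section 2.3.1 as risks of medication abortion itself, so a full listing would largely record expected effects. The aims in section 3 are to pilot a toolkit and understand satisfaction, and no safety objective is set. Nothing in section 9.4.4 forbids describing other AEs in the report. All of this is true. It explains why the omission is minor. It does not explain why data that must be collected in detail on 10 patients should have no planned display.

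**On routing.** This objection is stronger. Section 4.1 makes the family planning fellow responsible for facilitating evaluation and treatment when abnormal symptoms arise, and lets patients page the fellow directly at any hour. Section 9.4.2 places the pharmacist's one-week contact under the primary efficacy analysis, which implies that its findings are study data. Sections 10.1.4 and 10.1.5 provide for periodic verification and for data collection by trial staff under the PI. The toolkit's follow-up protocol, the interview guides and the collaborative practice agreement were not available, and any of them may state the step. Section 10.1.2 was also not in the text available, so nothing is inferred from it.

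What stands is narrow. None of the sections read says who passes on the pharmacist's one-week findings, or when. Nor do they say whether the fellow belongs to the study team.

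**A tempting stronger reading.** A reader might infer that the plan has no AE capture process, or that events handled by pharmacists will be lost. The documents do not support this. Section 8.3.4 requires capture of all AEs and names several routes.

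**Conclusion.** The concern holds as a minor point whose remedy is cheap. The table restriction is certain from the text: a non-serious AE in a patient who stays in the pilot has no place in any planned study result. The missing hand-off is less certain. It rests on the sections read and on the assumption that the unseen toolkit, practice agreement and guides do not supply it.

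The size cannot be put more closely than 0 to 10 patients, and the documents do not allow an estimate of how often, or how late, a pharmacist-handled event would miss the record.

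Two further inferences should be resisted:

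- A reader might say that an empty table would be a false zero. It would be a correct count of serious and discontinuation AEs. Comparing it with an assumed count of all AEs compares different quantities and shows no error.
- A reader might infer very long delays, because interviews follow the end of recruitment. That fits poorly with the 6-week participant duration in the synopsis and with section 4.2, which makes the interview part of a participant's completion.

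**What to change.** 1. In section 9.4.4, replace the restricted table with a by-patient listing of every recorded AE: onset, severity, relatedness, action taken, and whether a pharmacist or a physician managed it. Mark serious AEs and those leading to discontinuation, so that nothing now planned is lost. State the number of patients referred to a physician.
2. In section 8.3.4, have the research coordinator, a role already used in section 7.3, obtain the pharmacist's clinical notes from the one-week contact and from any pager call, and enter AEs from them. A physician then grades each event, consistent with the requirement there that relationship be judged by those qualified to diagnose. If the toolkit or practice agreement already states such a step, a cross-reference is enough.

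Using the notes is preferable to separate research-team telephone calls, which would run alongside the start-to-finish pharmacist follow-up that patients are later interviewed about.

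The cost is a little extra data handling for 10 patients. Onset, severity and relatedness are already required; action taken and who managed the event are the added items. Treatment, sample size, interviews, IRB reporting, the fellow route and the four-week test stay as they are.

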#### 9.4.5 BASELINE DESCRIPTIVE STATISTICS

Not applicable

#### 9.4.6 PLANNED INTERIM ANALYSES

Interim analyses are not planned during this short pilot study.

### 10 SUPPORTING DOCUMENTATION AND OPERATIONAL CONSIDERATIONS

#### 10.1 REGULATORY, ETHICAL, AND STUDY OVERSIGHT CONSIDERATIONS

##### 10.1.1 STUDY DISCONTINUATION AND CLOSURE

This study may be temporarily suspended or prematurely terminated if there is sufficient reasonable cause. Written notification, documenting the reason for study suspension or termination, will be provided by the suspending or terminating party to study participants, investigator and funding agency. If the study is prematurely terminated or suspended, the Principal Investigator (PI) will promptly inform study participants, the Institutional Review Board (IRB), and sponsor and will provide the reason(s) for the termination or suspension. Study participants will be contacted, as applicable, and be informed of changes to study visit schedule.

Circumstances that may warrant termination or suspension include, but are not limited to:

- Determination of unexpected, significant, or unacceptable risk to participants

- Demonstration of efficacy that would warrant stopping
- Insufficient compliance to protocol requirements
- Data that are not sufficiently complete and/or evaluable
- Determination that the primary endpoint has been met
- Determination of futility

Study may resume once concerns about safety, protocol compliance, and data quality are addressed, and satisfy the sponsor and/or IRB.

#### 10.1.3 SAFETY OVERSIGHT

Safety oversight will be monitored by the study PI.

#### 10.1.4 CLINICAL MONITORING

Data verification will take place periodically. This will ensure data completeness and monitor safety of participants.

#### 10.1.5 DATA HANDLING AND RECORD KEEPING

##### 10.1.5.1 DATA COLLECTION AND MANAGEMENT RESPONSIBILITIES

Data collection is the responsibility of the clinical trial staff at the site under the supervision of the PI. The investigator is responsible for ensuring the accuracy, completeness, legibility, and timeliness of the data reported.

##### 10.1.5.2 STUDY RECORDS RETENTION

Study documents will be retained for 2 years after the formal completion of the study.

#### 10.1.6 PROTOCOL DEVIATIONS

It is the responsibility of the PI to use continuous vigilance to identify and report deviations. Protocol deviations must be sent to the reviewing Institutional Review Board (IRB) per their policies. The site investigator is responsible for knowing and adhering to the reviewing IRB requirements.

